7 SYNOPSIS

This is a synopsis. The body of the protocol must be referenced for the complete study information.					
Study Title: An Open-Label, Safety and Pharmacokinetic Study of Hydromorphone Hydrochloride Extended-Release Tablets (Once-Daily Hydromorphone) in Opioid-Tolerant Pediatric Subjects with Chronic Pain					
Protocol Number	COV02520124	Phase	3b	Type	Interventional
Condition/Disease: Subjects 7 to 17 years old with chronic pain secondary to cancer and/or noncancer origins.					
Approximate					
Number of Subjects	100	Duration of Subject Participation		Approximately 28 days including an optional safety observation extension of up to 3 weeks.	
Number of Study Centers	Up to 10	Duration of Study		Five years.	
Rationale: This pediatric study is designed to provide safety information, dosing guidelines, and a pharmacokinetic (PK) evaluation of once-daily hydromorphone hydrochloride (HCl) extended-release (ER) tablets in children with chronic painful conditions who are “opioid-tolerant” prior to enrollment under the Pediatric Research Equity Act of 2003. Population PK techniques will be utilized in order to better understand the PK profile of once-daily hydromorphone HCl ER tablets in pediatric subjects while limiting the number and timing of sample collections.					
Objectives:					
Primary					
The primary objective of this study is to evaluate the safety (based on vital signs, pulse oximetry, clinical laboratory assessments, and adverse events [AEs]) of once-daily dosing of hydromorphone HCl ER tablets in pediatric subjects between 7 and 17 years old with pain secondary to cancer and/or noncancer origins.					
Secondary					
The secondary objectives of this study are to evaluate the following parameters:					

 • PK data following initial and steady-state dosing in subjects between 7 and 17 years old (in even distribution of age strata, for example, age 7 to less than 12 years and age 12 to 17 years). • Effectiveness (based on pain intensity scores) in controlling pain. • Quality of life utilizing a validated pediatric testing instrument (Pediatric Quality of Life [PedsQL]). 					
Design: This is an open-label, multidose, multicenter study for safety, PK, and efficacy of hydromorphone HCl ER in an opioid tolerant pediatric population 7 to 17 years of age with chronic pain secondary to cancer and/or noncancer origins.					
Subjects with continuous, around-the-clock opioid treatment with at least 6 mg of daily hydromorphone (or other opioid equivalents) for 5 or more days (ie, opioid tolerant) will be evaluated for study qualification at screening (Visit 1).					
On the morning of Day 1 (Visit 2), qualified subjects will switch from their current therapy to receive the first dose of hydromorphone HCl ER at the clinic with a dose strength matching 66% of their prior opioid dosage based on the protocol-provided conversion table. Subjects will remain at the clinic for up to 24 hours for safety and efficacy assessments and blood sampling. Subjects will continue to receive once daily hydromorphone HCl ER for 7 (± 2) days. No increase or decrease in hydromorphone HCl ER dose will be allowed. In the event of uncontrolled pain, 5 mg of immediate release oxycodone can be used as rescue therapy at 1 to 2 tablets per dose up to 5 times per day depending on the strength of hydromorphone HCl ER received.					

Subjects will return to the clinic on Day 7 (\pm 2 days) (Visit 3), take hydromorphone HCl ER in the morning, and stay for 12 hours while completing all remaining procedures and assessments before exiting the study (or proceeding to the optional safety extension).

As safety assessments, vital signs and pulse oximetry measurements will be conducted at scheduled visits and adverse events will be collected throughout the 7 (\pm 2) days of the treatment period. In addition, clinical laboratory evaluations will be performed at Screening (Visit 1) and study exit (Visit 3).

Sparse blood sampling of a subset of subjects for the measurement of plasma hydromorphone and hydromorphone-3- β -D glucuronide metabolite concentrations will take place on Day 1 (Visit 2) at the following time points: predose, between 4 to 6 hours, 7 to 9 hours, 14 to 18 hours, and 22 to 24 hours postdose; and on Day 7 (\pm 2 days) (Visit 3) at the following time points: predose and between 8 to 12 hours postdose.

Pain intensity ratings will be recorded by subject on the electronic diary at Screening (Visit 1); on Day 1 (Visit 2) at the following time points: predose (within 15 minutes of initial dosing), and 1, 2, 4, 6, and 8 hours (\pm 15 minutes) postdose; on Days 2-6 (\pm 2) at the following time points: predose (within 15 minutes of dosing) and prior to bedtime; on Day 7 (\pm 2): predose (within 15 minutes of dosing). Age-appropriate pain scales will be used for the study, i.e. Faces Pain Scale – Revised (FPS-R) is for 7 to less than 12 years and Visual Analog Scale (VAS) is for 12 to 17 years.

A quality of life (PedsQL) questionnaire will also be completed on Day 1 (Visit 2) predose and at study exit/Day 7 (Visit 3).

Subjects who complete the 7 (\pm 2) days of treatment have the option to extend hydromorphone HCl ER usage for pain relief and safety observation for up to 3 additional weeks per investigator's discretion.

Dose adjustment is allowed during this period. Subjects will visit the clinic weekly for continued eligibility assessment, safety evaluation, drug accountability (return and dispense), and/or dose adjustment. Subjects will visit the clinic at the end of safety observation extension for final assessment within 2 days after the last dose of hydromorphone HCl ER.

Subjects will be contacted by the site for a follow-up phone call at 7 (\pm 1) days after the study exit (Visit 3) or the last dose of extended hydromorphone HCl ER usage.

Inclusion Criteria: For inclusion into the study at screening (Visit 1), subjects must:

1. Be adequately informed and understand the nature and risks of the study and must be able to provide a signature and date on the informed assent form if appropriate, to participate. Parent(s)/legal guardian must provide written approval to participate.
2. Be male or female subjects aged 7 to 17 years, inclusive.
3. Be opioid-tolerant with chronic cancer or noncancer pain requiring continuous, around-the-clock oral or injectable opioid treatment. Opioid-tolerant is defined as having received a stable dose of regularly scheduled opioid or opioid combination products (including a regular rescue medication regimen) equivalent to least 6 mg of oral hydromorphone (see [Table 15-1](#) for opioid dose conversion) per day for at least 5 days prior to first dose.
4. (Female subjects of childbearing potential) Have a negative serum pregnancy test result at screening and a negative urine pregnancy test result on Day 1 (Visit 2). Those subjects who are sexually active (as determined by the investigator or designee) must be surgically sterilized (eg, hysterectomy or bilateral tubal ligation) at least 12 months prior to screening or use 1 of the following methods of birth control at least 30 days prior to screening and for the duration of study participation: hormonal contraception, intrauterine contraceptive device, or spermicide with barrier method (condom, cervical cap, or diaphragm). Subjects should continue contraception for at least 30 days after the last dose of study drug.
5. (Male subjects with reproductive potential who are sexually active as determined by the investigator or designee) Agree to use an acceptable method of contraception for the duration of the study (vasectomy or condom with spermicide).
6. Have established a favorable response to opioid therapy in reducing pain.

7. Require a minimum dose of 4 mg (1 JURNISTA tablet) and a maximum dose of 16 mg (1 hydromorphone HCl ER tablet) after determining 66% of the converted dose of hydromorphone HCl per day from an established conversion table (Table 15–1).
8. Be able to swallow a whole tablet without breaking, crushing, chewing or dissolving.
9. Be expected to require extended opioid treatment for at least 1 week.
10. Be able to communicate effectively with study personnel.
11. (Subjects and parents/legal guardian) Be able and willing to follow all protocol requirements and study restrictions.

Exclusion Criteria: Subjects will be ineligible for the study if any of the following criteria are present:

1. Have a life expectancy of less than 4 weeks.
2. Have a history of allergy or any significant intolerance with opioid treatment or **allergies** to sulfites as determined by the investigator or designee.
3. Are currently managed with opioid (transcutaneous) analgesic patches.
4. Have a history of drug or alcohol dependence.
5. Have a history of renal, hepatic, cardiovascular, or respiratory conditions that would contraindicate their participation in this study as determined by the investigator or designee.
6. Plan to undergo a surgical procedure within 3 days of Day 1 and for the duration of participation in the study. Subjects undergoing minor surgical procedures (eg, central line insertion, biopsies) will be eligible for participation in the study.
7. Exhibit hemodynamic instability as determined by the investigator or designee.
8. Have dysphagia or difficulty swallowing whole tablets as determined by the investigator or designee.
9. Have narrowing of the digestive tract, often due to esophageal strictures, Short Gut Syndrome, inflammatory bowel disease, peritonitis, cystic fibrosis, Meckel’s diverticulum, or past gastrointestinal surgery.
10. Have hypothyroidism, **Addison’s disease**, asthma (including exercise induced asthma) requiring daily inhalers, an **enlarged prostate**, **epilepsy**, low blood pressure, seizure disorder, high intracranial pressure, gallbladder problems, pancreatic disease, liver disease, or kidney disease.
11. Have an ileostomy or paralytic ileus.
12. Have had a blood-product transfusion within 2 weeks prior to screening (Visit 1) or expected to require transfusion during the study.
13. Participated in a study with any pain medication in the 2 weeks prior to screening (Visit 1). Subjects participating in other investigational studies are allowed.
14. Have a known history of human immunodeficiency virus, hepatitis C virus or hepatitis B virus.

Prior and Concomitant Treatment:

Subjects will be allowed to continue taking any nonprohibited prior medication/therapy if:

- The drug was started at least 14 days prior to first dose of study drug, AND
- The dose of medication is expected to remain unchanged for the duration of study participation.

Pertinent information for any medication taken during the study will be recorded.

Investigational Product and Administration:

- EXALGO (Hydromorphone HCl ER) 8-mg, 12-mg, and 16-mg tablets.
- JURNISTA (hydromorphone HCl ER) 4-mg tablets.

Tablets to be swallowed whole and not broken, chewed, dissolved, or crushed.

Rescue Medication:

- Immediate-release oxycodone (5 mg tablets).

Safety Assessment:

1. Physical examination.
2. Clinical laboratory tests.
3. Vital sign measurements.
4. Pulse oximetry measurements.
5. AEs.

Assessments:

1. The effectiveness endpoint is pain intensity measured on a FPS-R or VAS.
2. The health outcomes endpoint is quality of life, as measured by the PedsQL.

Pharmacokinetics:

Blood samples for the determination of plasma hydromorphone and hydromorphone-3- β -D glucuronide metabolite concentrations will be collected in selected windows of time: predose, 4 to 6 hours, 7 to 9 hours, 14 to 18 hours, 22 to 24 hours postdose on Day 1 (Visit 2); and predose and 8 to 12 hours postdose on Day 7 \pm 2 (Visit 3) in a subset of subjects.

Statistical Considerations:

Analysis Populations

The analysis populations include the following:

- The Safety Population will include all subjects who receive any quantity of study drug.
- The PK Population will consist of all subjects who receive at least 1 dose of study drug and have any samples collected after dosing at Visit 2 and/or Visit 3 that were analyzed for hydrocodone and hydromorphone-3- β -D glucuronide.
- The Modified Intent-To-Treat Population will consist of all subjects who receive study drug and who have at least 1 postdose pain intensity assessment.

Subject Characteristics

Demographic and baseline characteristics (including age, sex, race, ethnicity, weight, height, and medical history) will be summarized for the safety population by descriptive statistics. No statistical analyses will be performed.

Effectiveness and Health Outcomes Analysis

The endpoints below will be summarized at each assessment time point:

- Pain intensity with validated pain intensity scales FPS-R and VAS.
- Quality of life, as measured by the PedsQL.

Pharmacokinetic Analysis

A population PK dataset will be developed from the pooled pediatric and adult data from studies C-2005-013-01, C-2005-032-02 and 42801-PAI-1009 and the current study. Population PK analyses will be conducted via nonlinear mixed effect modeling using the nonlinear mixed-effects modeling software NONMEM[®], Version 7 or higher (ICON Development Solutions, Hanover, MD). A covariate analysis will be undertaken to determine the contribution of demographic and disease characteristics to variability in hydromorphone PK. Individual predicted hydromorphone exposure metrics (apparent first-order terminal elimination rate constant, the apparent plasma terminal elimination half-life, the minimum plasma concentration at steady-state, the peak plasma concentration at steady-state, the average concentration at steady-state, and the area under the plasma time-concentration curve at steady-state) will be derived from estimated parameters from the final model.

Safety Analysis

Data listings will be provided for all protocol-specified safety data. The Medical Dictionary for Regulatory Activities (MedDRA Version 9.1 or higher) will be used to classify all AEs with respect to system organ class and preferred term. Numbers of subjects with treatment-emergent AEs will be summarized.

For vital signs and pulse oximetry, descriptive statistics will be provided at each scheduled time point, including study exit. Descriptive statistics will be provided on changes from baseline of these assessments at each scheduled time point after baseline. No formal statistical tests will be performed.

Ethical Considerations: The study will be conducted in compliance with applicable US Food and Drug Administration (FDA) regulations, International Council for Harmonisation (ICH) guidelines for Good Clinical Practice (GCP), and in accordance with generally accepted ethical principles for the conduct of human research such as the Declaration of Helsinki.

The institutional review board (IRB) must review and approve the protocol and informed assent/consent forms before any subjects are enrolled. Before any protocol-required procedures are performed, the subject must be able to provide a signature and date on the informed assent form (IAF), if appropriate, to participate. The subject's legal guardian or parent(s) must provide written approval to participate.

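### The Day 2-6 bedtime pain ratings have no time-matched rating on the prior opioid, so the bedtime summaries cannot show whether pain control held after the switch

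*Combined protocol and SAP*

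**What the plan says.** All references are to Section 7 (Synopsis) of the combined protocol and SAP.

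- **Design.** There is one arm: "This is an open-label, multidose, multicenter study for safety, PK, and efficacy of hydromorphone HCl ER in an opioid tolerant pediatric population". No concurrent control and no diary run-in are described.
- **Switch.** On the morning of Day 1, "qualified subjects will switch from their current therapy to receive the first dose of hydromorphone HCl ER at the clinic". The ER dose is set at 66% of the converted prior dosage and is fixed for the 7 (± 2) day period, with oxycodone available as rescue.
- **Ratings on the prior opioid.** The schedule opens with "Pain intensity ratings will be recorded by subject on the electronic diary at Screening (Visit 1"), with no time of day and no time since the last opioid dose. Day 1 follows: "predose (within 15 minutes of initial dosing), and 1, 2, 4, 6, and 8 hours" after dosing. Only the predose value comes before the switch.
- **Ratings at home, Days 2-6.** Two a day: "predose (within 15 minutes of dosing) and prior to bedtime". Day 7 has a predose rating only.
- **Objective and analysis.** A secondary objective is "Effectiveness (based on pain intensity scores) in controlling pain". For pain and quality of life, the Effectiveness and Health Outcomes Analysis says "The endpoints below will be summarized at each assessment time point". No pain baseline or pain change score is defined. The Safety Analysis does specify one for vital signs and pulse oximetry: "Descriptive statistics will be provided on changes from baseline of these assessments at each scheduled time point after baseline".

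**The concern.** Subjects enter on a stable opioid regimen with an established favorable response (inclusion criteria 3 and 6). A low pain score on ER may therefore only show that pain was already controlled. With no control arm, the most informative use of the pain data is to see whether control held after the move to a fixed dose derived from 66% of the prior dosage. That requires pain on the prior regimen, rated in the same way and at the same time of day.

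The morning series has such a value, though only one. The bedtime series has none. A reader who sets the bedtime scores beside the pre-switch scores will compare evenings with a morning, or with a Screening rating at an unstated hour. If evenings are usually worse, ER will seem to fail. If they are usually better, it will seem to help. More subjects would not cure this.

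**Working it through.** The plan states no power, effect size, SD or margin for pain, so there is no figure of its own to reproduce. The check is a count of the schedule, followed by an illustration.

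**1. Count of nominal ratings per subject** (from the Design section; Screening read as one rating)

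| Occasion | Prior opioid | Study drug |
|---|---|---|
| Screening | 1 | 0 |
| Day 1 predose | 1 | 0 |
| Day 1, hours 1, 2, 4, 6, 8 | 0 | 5 |
| Days 2-6 predose | 0 | 5 |
| Days 2-6 bedtime | 0 | 5 |
| Day 7 predose | 0 | 1 |
| Total | 2 | 16 |

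- Bedtime: 0 on the prior opioid against 5 on drug. Share without a match: 5/16 = 31% of on-drug ratings, or 5/11 = 45% of those after Day 1.
- Morning predose: 1 on the prior opioid against 6 on drug (Days 2-7).
- Effect of the ± 2 day window, if twice-daily rating runs up to the day before Visit 3: with Visit 3 on Day 5, 3 bedtimes among 5 + 3 + 3 + 1 = 12 on-drug ratings (25%); on Day 9, 7 among 5 + 7 + 7 + 1 = 20 (35%).

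**2. What the bedtime scores can identify.** Let M0 and B0 be a subject's usual morning and bedtime pain on the prior opioid, and M1 and B1 the same on ER. The only time-defined pre-switch value estimates M0, so the available contrast is

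B1 − M0 = (B1 − B0) + (B0 − M0).

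The first term is the change of interest and the second is the usual evening-morning difference. B0 is not scheduled to be measured, so the two cannot be separated. Borrowing the evening-morning difference seen on ER does not help: (B1 − M0) − (B1 − M1) = M1 − M0, which is simply the morning change again.

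**3. Illustration of size.** These inputs are assumptions, not document figures: VAS scored 0-100, within-subject SD s of 10 to 25, independent rating errors, and no variation between subjects in true change. I take n = 50 on one scale (about 100 subjects, split evenly over two age strata with different scales). For the mean of 5 bedtime ratings minus the mean of k baseline ratings,

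SE = s × √((1/k + 1/5)/n).

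- With k = 1 and s = 10, SE = 10 × √(1.2/50) = 1.55. With s = 25, SE = 3.87.
- With no true drug difference and bedtime pain 5 points above morning pain, a 95% interval for bedtime minus Day 1 predose would exclude zero in 90% (s = 10) to 25% (s = 25) of such studies. With a 2-point shift the range is 25% to 8%.
- With matched bedtime baselines the shift drops out. The 95% half-width (1.96 × SE) goes from 3.04 with k = 1 to 2.02 with k = 3 (s = 10), or from 7.59 to 5.06 (s = 25).

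**4. Morning series, same assumptions.** Against the mean of six on-drug mornings, going from one to three baseline mornings changes the variance of the change score from (1 + 1/6) = 1.17 s² to (1/3 + 1/6) = 0.50 s², a cut of 57%. Correlated daily ratings would make the gain smaller.

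**The case against.** The strongest reply is that the plan never proposes the faulty comparison. Pain is summarized by time point, with no baseline, change score or test, and prior-opioid pain is never named as a comparator. A description of absolute pain levels also fits the words of the objective. This stands. A reader might infer that a planned effectiveness analysis is biased or invalid, but the documents do not support that. The interval calculations above show what would follow if someone made the comparison; they are not an error rate of this trial.

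A reader might also infer that the morning ratings lack a usable baseline. They do not: the Day 1 predose rating and the Day 2-7 ratings all precede that morning's dose. That baseline is thin, being a single day, but it is like for like.

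Nor is it right that the data are silent on the matter. The Screening rating gives a partial check on an unusual Day 1 value, and Days 2-6 show the evening-morning difference on ER. Neither supplies the bedtime level on the prior opioid.

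Open-label rating, rescue use and natural course would stay mixed with the drug effect even with a matched baseline. This stands too, and limits what the change can deliver.

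Finally, safety is the primary objective, and the Synopsis defers to the protocol body for full detail. A pre-switch diary described there cannot be excluded.

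**Conclusion.** The point holds for the bedtime series. Nominally 5 of 16 on-drug ratings (31%) have no time-matched value on the prior opioid, and none can be recovered later. The bedtime summaries can describe pain levels on ER, but they cannot show whether control held after the switch. No planned test, sample size or decision rule is affected. The matter is how well a secondary objective can be interpreted, and the change is a cheap improvement, not the repair of an error.

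The conclusion rests on reading Screening as one rating not fixed at bedtime, and on the Synopsis schedule being complete. The size of any evening-morning difference is not in the documents, so the amount of distortion is unknown. The gain from averaging depends on how many pre-switch days exist and on how strongly daily ratings are correlated.

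**What to change.** - Let subjects keep using the electronic diary after Screening, where it is already in use. Require a bedtime rating at least on the evening before Day 1.
- Where the Screening-to-Day 1 interval allows, collect morning (before the scheduled opioid) and bedtime ratings on up to 3 pre-switch days. Criterion 3 already requires at least 5 days of stable dosing before the first dose, so these days fall on a stable regimen.
- Define separate morning and bedtime baselines in advance, and say whether the Day 1 predose rating is averaged into the morning one. Describe Days 2-7 against the matching baseline, with rescue use shown alongside.
- If the protocol body already contains a pre-switch diary, bring the Synopsis into line with it.

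The cost is 1 rating per subject at the minimum and 3 × 2 = 6 at most, with no added visit or procedure. Subjects whose Screening is close to Day 1 will have fewer baseline ratings, so the number available should be reported.

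### Do the 6 mg/day opioid-tolerance threshold and the 4 mg minimum study dose exclude each other at the boundary?

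*Combined protocol and SAP*

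**What the plan says.** All the relevant text is in Section 7, Synopsis.

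- **Design, tolerance threshold:** subjects have been on "at least 6 mg of daily hydromorphone (or other opioid equivalents) for 5 or more days".
- **Inclusion criterion 3:** a stable, regularly scheduled opioid regimen "equivalent to least 6 mg of oral hydromorphone" per day. The threshold is inclusive.
- **Design, first dose:** subjects switch on Day 1 to hydromorphone ER "with a dose strength matching 66% of their prior opioid dosage based on the protocol-provided conversion table".
- **Inclusion criterion 7:** subjects must "Require a minimum dose of 4 mg (1 JURNISTA tablet) and a maximum dose of 16 mg", and this is judged "after determining 66% of the converted dose of hydromorphone HCl per day". Each limit is also expressed as one tablet.
- **Investigational Product and Administration:** 4 mg tablets under one brand and 8, 12 and 16 mg tablets under another, all to be swallowed whole.

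The Synopsis gives no rule for rounding the 66% result to a tablet. It sends the reader to the protocol body for complete information, and criteria 3 and 7 both point to Table 15-1 for the conversion.

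**The concern.** The lowest qualifying prior dose and the lowest study dose look as if they were meant to correspond, and at the stated factor they do not quite do so. A subject at exactly 6 mg/day passes criterion 3, but 66% of that dose is below the minimum in criterion 7. If sites read this differently, one might enrol such a child and another might record a screen failure. A child enrolled on the lenient reading could later be called an eligibility deviation on the strict one.

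The point deserves a check because the mismatch falls on a round number that is itself the named threshold. The same calculation also sets the first dose, which is then fixed for the 7 (±2) day treatment period.

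**Working it through.** **Inputs (all from the Synopsis).** Threshold 6 mg/day (Design; criterion 3). Factor 66% (Design; criterion 7). Study-dose limits 4 and 16 mg (criterion 7). Strengths 4, 8, 12 and 16 mg, whole tablets only (Investigational Product and Administration).

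**Step 1: the plan's own figure.** Factor × threshold = 0.66 × 6 = 3.96 mg. To the nearest milligram this is the stated 4 mg. Unrounded, it is 4 − 3.96 = 0.04 mg short, and 0.04/4 = 1%.

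**Step 2: the strict reading.** With no rounding, criterion 7 is met for prior doses from 4/0.66 = 6.06 to 16/0.66 = 24.24 mg/day. The conflict with criterion 3 is therefore limited to 6.00 to below 6.06 mg/day.

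**Step 3: can the strict reading be applied to dosing?** A prior dose gives an available strength exactly only at 4/0.66, 8/0.66, 12/0.66 and 16/0.66, that is 6.06, 12.12, 18.18 and 24.24 mg/day. Other prior doses do not:

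| Prior dose (mg/day) | 66% of it (mg) | Nearest strength (mg) |
|---|---|---|
| 6 | 3.96 | 4 |
| 7 | 4.62 | 4 |
| 8 | 5.28 | 4 |
| 10 | 6.60 | 8 |
| 12 | 7.92 | 8 |
| 18 | 11.88 | 12 |
| 24 | 15.84 | 16 |

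Some matching step is therefore needed for nearly everyone. The Design wording, which speaks of a strength that matches the 66% figure, and criterion 7, which states its limits as tablets, both fit that.

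**Step 4: sensitivity to the convention (assumptions, since none is stated).**

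- Nearest milligram or nearest tablet: 6 mg/day gives 4 mg, and nobody is caught between the criteria.
- Two-thirds in place of 0.66: 2/3 × 6 = 4.00 mg, and the four strengths correspond to 6, 12, 18 and 24 mg/day. That 66% is shorthand for two-thirds is an inference; the text does not say so.
- Strict rounding down: 3.96 mg has no tablet, and the misfit at 6 mg/day remains.

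**Step 5: does it reach the analysis?** The Safety Population is defined by receipt of any study drug. The PK Population is defined by dosing plus analysed post-dose samples, and the Modified Intent-To-Treat Population by dosing plus one post-dose pain rating. None refers to criterion 3 or 7. The Synopsis describes summaries and population PK modelling, and ties no power or sample-size figure to the dose floor.

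**The case for a change.** The strongest reply is that, read literally, criterion 7 makes the 6 mg figure idle: anyone who passes it is already at 6.06 mg/day or more. On that view either the published threshold has no effect or 66% is not meant literally, and either way the wording is off. Rounding also leaves the upper end open. Unrounded, the ceiling is 24.24 mg/day. Rounded to the nearest milligram, results below 16.5 mg count as 16, so it approaches 16.5/0.66 = 25 mg/day. Rounded to the nearest tablet, no higher strength exists to bound it. This concerns children on opioids, and the correction would take one line.

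Part of this stands. The Synopsis does not say whether the 4 to 16 mg limits apply before or after matching to a tablet, and the figures do not align exactly at the threshold. It does not amount to a contradiction, for two reasons. Inclusion criteria apply jointly: one defines opioid tolerance and the other limits the study dose, so passing one and failing the other would be an ordinary screen failure. A deviation would arise only if such a subject were enrolled anyway. The idle-threshold argument also depends on the unrounded reading. With matching to the nearest tablet, the 6 mg floor in criterion 3 does decide entry at the low end. The open ceiling is the same unstated convention seen from the other end, and the Synopsis may not be where it is defined.

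**Conclusion.** The concern does not call for a change. Its arithmetic is correct: 3.96 mg against 4 mg, a gap of 0.04 mg or 1%, affecting at most prior doses from 6.00 to below 6.06 mg/day. The documents do not say how many subjects would fall there. The gap disappears under nearest-milligram or nearest-tablet matching, and some matching is unavoidable with whole tablets in four strengths. It persists only if no rounding, or strict rounding down, is assumed.

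This is a missing convention that sites can be expected to fill sensibly, and settling it would alter no analysis population, planned summary or conclusion. The judgement rests on the Synopsis alone; the protocol body and Table 15-1 may already state the convention, so its absence from the plan cannot be asserted. Which figure or rounding direction is clinically right is for the sponsor, and no view is taken on it here.

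### The PK Population definition names hydrocodone, although the study gives, samples and models hydromorphone

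*Combined protocol and SAP*

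**What the plan says.** In the Synopsis, under Statistical Considerations, Analysis Populations, a subject belongs to the PK Population after receiving study drug, provided that they "have any samples collected after dosing at Visit 2 and/or Visit 3 that were analyzed for hydrocodone" and for the hydromorphone 3-glucuronide.

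The other PK statements in the Synopsis name hydromorphone:

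- **Rationale:** population PK methods are used to "better understand the PK profile of once-daily hydromorphone HCl ER tablets in pediatric subjects".
- **Design:** "Sparse blood sampling of a subset of subjects for the measurement of plasma hydromorphone" and its 3-glucuronide, on Day 1 and Day 7.
- **Pharmacokinetics:** "Blood samples for the determination of plasma hydromorphone" and the same metabolite, in the same windows.
- **Pharmacokinetic Analysis, covariates:** the aim is to determine the "contribution of demographic and disease characteristics to variability in hydromorphone PK".
- **Pharmacokinetic Analysis, derived quantities:** "Individual predicted hydromorphone exposure metrics" are to be obtained from the final model.

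The Investigational Product section lists only hydromorphone ER tablets, and the rescue medication is oxycodone.

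**The concern.** Hydrocodone and hydromorphone are different opioids with similar names. An analysis-set definition is an instruction: a programmer applies it to the data and a reader of the report relies on it to know who was counted. If the analyte in that instruction is one the study does not plan to measure, the rule either selects nobody or has to be set aside by whoever programs it. PK after initial and steady-state dosing is the first secondary objective listed, so its analysis set should work as written. Because one opioid name replaces another, the slip is also easy to miss for someone outside the study team.

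**Working it through.** The plan gives no figure to reproduce here. The check compares the text and counts the planned samples.

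**1. What is administered, measured and modelled**

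| Place in the Synopsis | Drug or analyte named |
|---|---|
| Investigational Product | hydromorphone (4, 8, 12 and 16 mg ER tablets) |
| Rescue Medication | oxycodone |
| Design, blood sampling | hydromorphone and its 3-glucuronide |
| Pharmacokinetics, blood sampling | hydromorphone and its 3-glucuronide |
| PK Analysis, covariates | hydromorphone |
| PK Analysis, exposure metrics | hydromorphone |
| Analysis Populations, PK Population | **hydrocodone** and the hydromorphone 3-glucuronide |

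Only the last row differs. It pairs hydrocodone with the glucuronide of hydromorphone, and in both sampling descriptions the parent drug in that position is hydromorphone.

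**2. Planned samples per PK-subset subject** (Design and Pharmacokinetics agree)

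- Visit 2: predose, 4–6 h, 7–9 h, 14–18 h, 22–24 h = 5
- Visit 3: predose, 8–12 h = 2
- Total: 5 + 2 = 7

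Planned for hydromorphone and its 3-glucuronide: 7 of 7. Planned for hydrocodone: 0 of 7. The rule joins its two analytes with *and*, so under the assays described no sample satisfies it.

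**3. The rule with the word corrected**

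By the window labels, the postdose samples are 4 at Visit 2 and 1 at Visit 3, so 4 + 1 = 5. Any one of them, if analyzed, would qualify a dosed subject. The Visit 3 predose sample is also drawn after the Visit 2 dose, so a looser reading counts 5 + 1 = 6. The finding does not depend on which count is used.

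**4. Other explanations considered**

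- *Extraction fault or redaction:* the word is a complete, correctly spelled drug name.
- *Superseded text:* the sentence stands in the current definition, not in a summary of changes.
- *A deliberate assay for a previous opioid:* subjects arrive on other opioids, and hydrocodone could be among them, but no such assay is described. It would also be an odd entry condition for the PK set of a hydromorphone study.

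The size of the PK subset is not stated, so the effect cannot be given as a number of subjects.

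**The case against.** The strongest reply is that this is a proofreading slip with no demonstrated effect.

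- **It is only a synopsis.** The Synopsis itself refers the reader to the protocol body for complete information, and the body may already be correct. That is fair and could not be checked here. It is a reason to check the body and the SAP, but the Synopsis sentence is still wrong.
- **An empty set is not proved.** The Synopsis describes intended measurements, not the full bioanalytical panel. This stands as a qualification: the supported statement is that no hydrocodone assay is described, so no planned sample meets the rule.
- **Nothing depends on it.** The modelling is introduced with "A population PK dataset will be developed from the pooled pediatric and adult data" from three named earlier studies and the current one, without reference to the PK Population. No hypothesis test uses the set, and the Safety and Modified Intent-To-Treat Populations are unaffected. This stands in full and keeps the severity low.
- **The intent is obvious.** It is, and that makes the correction uncontroversial. A definition that works only if the reader silently substitutes another drug name still needs correcting.

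**Conclusion.** The concern holds, as a minor point. The PK Population definition names the wrong analyte and contradicts the study drug, both sampling descriptions and the planned analyses. Read literally, 0 of the 7 planned samples per PK-subset subject would count towards membership.

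The effect is confined to the definition and reporting of the named PK Population. It does not threaten the population PK model, and no sample size or test result changes. The conclusion assumes that the assays described in the Synopsis are the ones to be run, and it makes no claim about the wording of the protocol body or the SAP.

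**What to change.** In the PK Population definition, replace hydrocodone with hydromorphone and leave the rest of the rule unchanged. Then confirm that the protocol body, the SAP and any programming specification use the corrected wording.

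The cost is one word in the Synopsis and a wording check elsewhere. No sample, visit, assay or stated number changes.
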